APPENDIX I: SCHEDULE OF EVENTS

| | STUDY VISITS ^A | | | | | | | | | | | | |
|---|---------------------------------------|--------------------|-----------|--------|--------|----------------|--------|----------------|---------|----------------|---------|----------------|------------------------------|
| | Screening Phase (Week -6 to Day 0) | Double-Label Phase | | | | | | | | | | | Follow-Up Phase |
| | | M0/ Day 1 | Day 14 | M 1 | M 3 | M 6 | M 9 | M 12 | M 15 | M 18 | M 21 | M24/ ET/EOT | M25/ 4 Wks post ET/EOT |
| Study Procedures | | | | | | | | | | | | | |
| Informed Consent | X | | | | | | | | | | | | |
| Eligibility Criteria | X | | | | | | | | | | | | |
| Medical and Surgical History | X | | | | | | | | | | | | |
| Medication/Therapy Record | X | X | X | X | X | X | X | X | X | X | X | X | X |
| Vital Signs | X | X | X | X | X | X | X | X | X | X | X | X | X |
| Physical Examination (including weight, height at screening only) | X | | | | | | | X | | | | X | X |
| Chest X-ray | X | | | | | | | | | | | | |
| 12 Lead ECG | X | | | | | | | X | | | | X | |
| Liver and Abdominal Ultrasound | X ^B | | | | | X ^C | | X ^C | | X ^C | | X | |
| Liver Biopsy | X ^D | | | | | X ^E | | X ^F | | X ^E | | X ^F | |
| Transient Elastography (at select centers only) | X | | | | | X | | X | | X | | X | |
| Study Drug Administration/Dispense Study Drug | | X | X | X | X | X | X | X | X | X | X | | |
| Compliance Assessment (Capsule Count) | | | X | X | X | X | X | X | X | X | X | X | |
| Adverse Event Assessment | | X | X | X | X | X | X | X | X | X | X | X | X |
| Clinical Laboratory Evaluations | | | | | | | | | | | | | |
| Hematology | X | X | | X | X | X | X | X | X | X | X | X | X |
| Chemistry | X | X | X | X | X | X | X | X | X | X | X | X | X |
| Coagulation | X | X | | X | | X | | X | | X | | X | X |
| Urinalysis | X | X | | | | X | | X | | X | | X | X |
| Immunosuppressant Concentration Monitoring | | X | X | | | | | | | | | | |

Title: A Multicenter, Double-Blind, Randomized Trial of IDN-6556 in Subjects Who had Hepatitis C Virus (HCV) Reinfection and Liver Fibrosis or Cirrhosis following Orthotopic Liver Transplantation for Chronic HCV Infection and Who Subsequently Achieved a Sustained Virologic Response Following anti-HCV Therapy

| | STUDY VISITS ^A | | | | | | | | | | | | |

^G Blood samples will be taken at predose, and at 0.5, 1, 2, 3, 4, 5, and 8 hours post dose for immunosuppressant pharmacokinetic analysis.

^H If elevations in α-fetoprotein occur during the study, Investigators should utilize normal clinical practice for follow-up of subjects and discuss treatment (dis)continuation with the Conatus Medical Monitor.

^I ELF test to be run every 6 months only.

^J Blood samples will be taken at predose, and at 0.5, 1, 2, 3, 4, 5, and 8 hours post dose for pharmacokinetic analysis. The time window for samples will be:

Title: A Multicenter, Double-Blind, Randomized Trial of IDN-6556 in Subjects Who had Hepatitis C Virus (HCV) Reinfection and Liver Fibrosis or Cirrhosis following Orthotopic Liver Transplantation for Chronic HCV Infection and Who Subsequently Achieved a Sustained Virologic Response Following anti-HCV Therapy

- 0.5 hour ± 5 minutes
- 1 hour ± 5 minutes
- 2 hour ± 5 minutes
- 3 hour ± 10 minutes
- 4 hour ± 10 minutes
- 5 hour ± 10 minutes
- 8 hour ± 10 minutes

^K If repeat laboratory testing is required for elevated ALT, AST, and/or total bilirubin (refer to Section 8.1.9) a single blood sample will be taken for pharmacokinetic analysis.

^L For women of childbearing potential only.

Title: A Multicenter, Double-Blind, Randomized Trial of IDN-6556 in Subjects Who had Hepatitis C Virus (HCV) Reinfection and Liver Fibrosis or Cirrhosis following Orthotopic Liver Transplantation for Chronic HCV Infection and Who Subsequently Achieved a Sustained Virologic Response Following anti-HCV Therapy

APPENDIX II: LIVER BIOPSY SCORING AND ASSESSMENT

Ishak Modified Histological Activity Index (Ishak Fibrosis Score)

Liver biopsy findings are assigned scores for fibrosis as follows:

Table II.1 Ishak Fibrosis Score: Architectural Changes, Fibrosis and Cirrhosis

| | Score |
|--|-------|
| No fibrosis | 0 |
| Fibrous expansion of some portal areas, with or without short fibrous septa | 1 |
| Fibrous expansion of most portal areas, with or without short fibrous septa | 2 |
| Fibrous expansion of most portal areas, with occasional portal to portal bridging | 3 |
| Fibrous expansion of portal areas, with marked bridging (portal to portal as well as portal to central) | 4 |
| Marked bridging (portal to portal and/or portal to central) with occasional nodules (incomplete cirrhosis) | 5 |
| Cirrhosis probable or definite | 6 |

Ishak Modification of Knodell Histological Activity Index

Liver biopsy findings will be assigned scores for necro-inflammation as follows:

Table II.2 Ishak Modification of Knodell Histological Activity Index: Necro-inflammatory Scores

| | Score |
|--|-------|
| A Periportal or periseptal interface hepatitis (piecemeal necrosis) | |
| Absent | 0 |
| Mild (focal, few areas) | 1 |
| Mild/moderate (focal, most portal areas) | 2 |
| Moderate (continuous around <50% of tracts or septa) | 3 |
| Severe (continuous around >50% of tracts or septa) | 4 |
| B Confluent necrosis | |
| Absent | 0 |
| Focal confluent necrosis | 1 |
| Zone 3 necrosis in some areas | 2 |
| Zone 3 necrosis in most areas | 3 |
| Zone 3 necrosis + occasional portal-central bridging | 4 |
| Zone 3 necrosis + multiple portal-central bridging | 5 |

Title: A Multicenter, Double-Blind, Randomized Trial of IDN-6556 in Subjects Who had Hepatitis C Virus (HCV) Reinfection and Liver Fibrosis or Cirrhosis following Orthotopic Liver Transplantation for Chronic HCV Infection and Who Subsequently Achieved a Sustained Virologic Response Following anti-HCV Therapy

| | |
|---|---|
| Pan acinar or multiacinar necrosis | 6 |
| C Focal (spotty) lytic necrosis, apoptosis and focal inflammation | |
| Absent | 0 |
| One focus or less per 10X objective | 1 |
| Two – Four foci per 10X objective | 2 |
| Five – Ten foci per 10X objective | 3 |
| More than ten foci per 10X objective | 4 |
| D Portal Inflammation | |
| None | 0 |
| Mild, some or all portal areas | 1 |
| Moderate, some or all portal areas | 2 |
| Moderate/marked, all portal areas | 3 |
| Marked, all portal areas | 4 |

Title: A Multicenter, Double-Blind, Randomized Trial of IDN-6556 in Subjects Who had Hepatitis C Virus (HCV) Reinfection and Liver Fibrosis or Cirrhosis following Orthotopic Liver Transplantation for Chronic HCV Infection and Who Subsequently Achieved a Sustained Virologic Response Following anti-HCV Therapy

APPENDIX III: CLASSIFICATION OF HEPATIC AND RENAL IMPAIRMENT

Table III.1 Assessment of Hepatic Impairment: Child-Pugh Scale (adapted from Pugh et al)¹⁴

| | Points Scored for Observed Findings | | |
|-------------------------------------|-------------------------------------|-----------|----------|
| | 1 | 2 | 3 |
| Encephalopathy Grade ⁺ | None | 1 or 2 | 3 or 4 |
| Ascites | Absent | Slight | Moderate |
| Serum Bilirubin (mg/dL) | < 2.0 | 2.0 - 3.0 | > 3.0 |
| Serum Albumin (g/dL) | > 3.5 | 2.8 - 3.5 | < 2.8 |
| Prothrombin Time (sec prolonged) | < 4 | 4 - 6 | > 6 |
| Classification of clinical severity | | | |
| Class A: Score 5-6 (mild) | | | |
| Class B: Score 7-9 (moderate) | | | |
| Class C: Score 10-15 (severe) | | | |

***Hepatic Encephalopathy grading:**

- Grade 0: normal consciousness, personality, neurological examination, electroencephalogram
- Grade 1: restless, sleep disturbed, irritable/agitated, tremor, impaired handwriting, 5 cps waves
- Grade 2: lethargic, time-disorientated, inappropriate, asterixis, ataxia, slow triphasic waves
- Grade 3: somnolent, stuporous, place-disoriented, hyperactive reflexes, rigidity, slower waves
- Grade 4: unrousable coma, no personality/behavior, decerebrate, slow 2-3 cps delta activity

Determination of Encephalopathy for the Calculation of the Child-Pugh Score

Encephalopathy Test (If needed)

The number connection test will facilitate the diagnosis of hepatic encephalopathy. The test should be performed by the subject after the investigator's verbal instructions. The purpose is to correctly combine numbers with a pencil on a test chart as fast as possible. If the subject needs more than 40 seconds to perform the task, there is a strong indication of a latent hepatic encephalopathy.

Title: A Multicenter, Double-Blind, Randomized Trial of IDN-6556 in Subjects Who had Hepatitis C Virus (HCV) Reinfection and Liver Fibrosis or Cirrhosis following Orthotopic Liver Transplantation for Chronic HCV Infection and Who Subsequently Achieved a Sustained Virologic Response Following anti-HCV Therapy

Table III.2 Classification of Renal Function Based on GFR (eGFR) or Estimated Creatinine Clearance (CLcr)^a

| Stage | Description ^b | eGFR ^c (mL/min/1.73m ²) | CLcr ^d (mL/min) |
|-------|--------------------------------|---|-------------------------------|
| 1 | Control (normal) GFR | ≥ 90 | ≥ 90 |
| 2 | Mild decrease in GFR | 60 - 89 | 60 - 89 |
| 3 | Moderate decrease in GFR | 30-59 | 30 - 59 |
| 4 | Severe decrease in GFR | 15 - 29 | 15 - 29 |
| 5 | End Stage Renal Disease (ESRD) | <15 not on dialysis | <15 not on dialysis |
| | | Requiring dialysis | Requiring dialysis |

- a. In some situations, collection of 24-hour urine samples for measurement of creatinine clearance, or measurement of clearance of an exogenous filtration marker, may provide better estimates of GFR than the prediction equations. The situations include determination of GFR for patients in the following scenarios: undergoing kidney replacement therapy; acute renal failure; extremes of age, body size, or muscle mass; conditions of severe malnutrition or obesity; disease of skeletal muscle; or on a vegetarian diet.
- b. Stages of renal impairment are based on K/DOQI Clinical Practice Guidelines for Chronic Kidney Disease (CKD) from the National Kidney Foundation in 2002¹⁵; GFR: glomerular filtration rate
- c. eGFR: estimate of GFR based on an MDRD equation
- d. CLcr: estimated creatinine clearance based on the C-G equation

[figure not shown]
Title: A Multicenter, Double-Blind, Randomized Trial of IDN-6556 in Subjects Who had Hepatitis C Virus (HCV) Reinfection and Liver Fibrosis or Cirrhosis following Orthotopic Liver Transplantation for Chronic HCV Infection and Who Subsequently Achieved a Sustained Virologic Response Following anti-HCV Therapy

APPENDIX IV: FIBROSCAN® PROTOCOL

Background

Transient elastography performed with FibroScan® uses a low frequency vibrator (50Hz) mounted on 1-D US probe (5MHz). The speed of propagation of the shear wave through the liver is proportional to stiffness. The stiffness correlates with the severity of fibrosis^{16,17}.

Figure IV.1 FibroScan® Probe Placement in Relation to Anatomy of a Subject

Reproduced from Ziol et al 2005¹⁷.

There are three images displayed on the monitor:

1. A-mode image
2. Time movement (TM) image
3. A 2D elastogram

These images are used by the operator to make sure that the area of the liver selected is free of large vascular structures, that lung fields do not encroach on inspiration and that the selected area is not over a rib. The elastogram demonstrates the depth of the shear wave with time. The slope of the resulting line gives speed of propagation.

Title: A Multicenter, Double-Blind, Randomized Trial of IDN-6556 in Subjects Who had Hepatitis C Virus (HCV) Reinfection and Liver Fibrosis or Cirrhosis following Orthotopic Liver Transplantation for Chronic HCV Infection and Who Subsequently Achieved a Sustained Virologic Response Following anti-HCV Therapy

There are four figures displayed on the monitor:

1. The cumulative median liver stiffness value
2. The current liver stiffness value
3. The inter-quartile range
4. The success rate

Method

1. The subject is asked to lie comfortably in the supine position with his/her right arm fully abducted and resting on a pillow.
2. Cover the tip of the probe with a small amount of coupling gel and place on the skin, on the right lateral wall of the abdomen between the ribs at the level of the right lobe of the liver.
3. The right lobe of the liver is selected to ensure that the area of the liver to be measured is at least 6 cm thick.
4. The probe must be placed perpendicular to the subject's abdominal wall.
5. Pressure should be applied by the operator on the subject and the button is pressed to initiate an acquisition.
 - a. It is important to apply enough pressure on the subject so that the pressure bar display is within the green range. Insufficient pressure will be displayed as orange and over pressure will be displayed as red.
 - b. Pressure must be released immediately following an acquisition.
 - c. When making a measurement, it is also important to ensure that the subject is breathing slowly and not moving or speaking.

1 INTRODUCTION

Clinical protocol IDN-6556-07 describes the collection and analysis of clinical study data to evaluate the use of emricasan (IDN-6556) in subjects who had HCV reinfection and liver fibrosis or cirrhosis following orthotopic liver transplantation for chronic HCV infection and who subsequently achieved a sustained virologic response (SVR) following anti-HCV therapy. This document provides details of the statistical analyses to be performed. All decisions regarding handling of data for reporting results will be determined prior to database lock and will be described in the relevant sections of this statistical analysis plan (SAP).

2 STUDY OBJECTIVES

2.1 PRIMARY OBJECTIVE

The primary objective of this clinical trial is to assess the effect of oral emricasan on fibrosis or cirrhosis using the Ishak Fibrosis Score, in subjects with HCV reinfection and liver fibrosis or cirrhosis following orthotopic liver transplantation for chronic HCV who subsequently achieved SVR following anti-HCV therapy.

2.2 SECONDARY OBJECTIVES

The secondary objectives of this clinical trial are:

- To determine the effects of oral emricasan on necro-inflammatory sub-score of the modified Histological Activity Index
- To determine the effects of oral emricasan on markers of mechanism of action and inflammation
- To assess the safety and tolerability of oral emricasan in subject's status post orthotopic liver transplantation.

3 STUDY DETAILS

3.1 STUDY DESIGN

This is a double-blind, randomized, multicenter study involving subjects with chronic HCV who underwent liver transplantation; developed HCV-related liver fibrosis or cirrhosis; achieved SVR following anti-HCV therapy; and still show demonstrable fibrosis or cirrhosis on liver biopsy. Upon successful screening, subjects are randomized to receive 25 mg BID of emricasan or placebo in a 2:1 ratio.

The subjects are stratified based on the stage of fibrosis or cirrhosis at Baseline:

- Ishak F2
- Ishak F3-F5
- Ishak F6

The duration of each subject's participation will be approximately 26.5 months and will consist of:

- Screening period of up to 6 weeks
- Double-blind treatment period of 24 months
- A follow-up visit 4 weeks after completion of treatment

The schedule of events is provided in [Appendix 1](#) of the protocol.

3.2 STUDY POPULATION

Approximately 60 subjects who underwent orthotopic liver transplantation for chronic HCV, developed HCV-related liver fibrosis or cirrhosis, achieved a SVR with anti-viral treatment, and still have demonstrable fibrosis or cirrhosis on liver histology will be enrolled. Up to 15 subjects with an Ishak score of F6 can be enrolled.

3.3 RANDOMIZATION

The assignment to emricasan or placebo will be performed randomly in a 2:1 ratio to emricasan 25 mg BID or matching placebo BID. Approximately 60 subjects will be enrolled in this trial with 40 assigned to emricasan and 20 assigned to placebo. Randomization will be stratified based on baseline Ishak Fibrosis Score: F2, F3-F5, or F6.

The randomization schedule will be generated using a validated randomization program and verified for accuracy using strict quality control procedures. Randomization numbers and study drug assignment will be centrally coordinated through the study's Interactive Web Randomization System (IWRS).

3.4 BLINDING

This clinical trial is a double-blind study through the final study visit. The final randomization codes for each subject completing the trial will be provided after all subjects complete their final visit and database lock occurs.

Investigators will be able to unblind individual subjects through the IWRS when it is medically imperative to know whether a specific subject is receiving emricasan or placebo, such as in the occurrence of an adverse event (AE) that the Investigator feels cannot be adequately treated

without knowing the identity of the study drug. In the event of an individual subject being unblinded when medically imperative, the individual subject will have their study drug stopped sometime prior to unblinding. Every effort must be made to contact the Medical Monitor to discuss the case before breaking the blind, or if in an emergency, as soon as possible thereafter (no later than 24 hours after emergency unblinding) to inform the Medical Monitor that unblinding was performed but without disclosing the actual study drug assignment. The investigator should make arrangements to ensure that access to the secure internet site (i.e., individual user name and password) is maintained in strict confidence to prevent a compromise of subject blinding by non-study or unauthorized individuals.

The Sponsor may access the randomization codes for individual subjects with potential suspected unexpected serious adverse reactions (SUSARs) for regulatory reporting or for the purpose of evaluating an emergent safety issue. In such an event, the Sponsor will document the rationale, circumstances, and the person or persons being informed about the unblinding.

If the blind for an individual subject is broken (by the Investigator or the Sponsor), an entry must be made in the electronic data capture system that contains the reason that the blind was broken and the name of the person contacted at the Sponsor or designee.

3.5 STUDY VISIT ASSIGNMENTS

Study visits are designated on the electronic case report forms (eCRFs) and data will be analyzed per the study visit assigned and collected. All post-baseline biopsies will be assigned and collected on the Month 12 and 24 eCRFs.

For purposes of sensitivity analyses, biopsies will also be assigned to Month 12 and Month 24 flags, respectively, based on biopsy date. Biopsies will be classified as Month 12 biopsies flag if the biopsy date is collected within ± 8 weeks (i.e., ± 56 study days, inclusive) from the planned Month 12 visit date relative to the Day 1 visit date (i.e., Month 12 visit date – Day 1 visit date + 1). Similarly, Month 24 biopsies flag will designate those biopsies at Month 24 that are within ± 8 weeks (i.e., ± 56 study days, inclusive) from the planned Month 24 visit date relative to the Day 1 visit date (i.e., Month 24 visit date – Day 1 visit date + 1).

4 PLANNED SIZE DETERMINATION

This study will be conducted at multiple centers at which approximately 60 subjects will be enrolled and treated in a 2:1 ratio with emricasan or placebo, respectively. The sample size determination for this study is based on the Phase 2b screening methodology presented in [Fleming and Richardson \(2004\)](#).

The base case for the placebo response rate of 30% was assumed and obtained from [George, et al \(2009\)](#), where it stated that 29% of patients showed a response in fibrosis from a mean of 1.6 years following HCV-SVR.

Treatment duration for all subjects is expected to be two years. The primary analysis of this Phase 2 “screening” study is formally based on a three-category decision guideline. The decision guideline for this study is based on whether the difference in the proportions of subjects who show a response (i.e., improvement or no change) per their Ishak Fibrosis Score at 24 months for emricasan compared to placebo is less than 5%, is from 5% up to 15%, or is more than 15%. Specifically, the outcome of the study will determine one of the following three course of action:

1. If the difference in response rates between emricasan and placebo (i.e., emricasan response rate – placebo response rate) is less than 5%, then emricasan regimen is not plausibly more efficacious than placebo; hence, emricasan or its utility in this indication will be reconsidered.
2. If the difference in response rates between emricasan and placebo is from 5% up to 15%, then emricasan is plausibly more efficacious than placebo in this indication if secondary analyses of biomarkers suggest utility of emricasan or a positive safety profile is observed; hence, emricasan could be evaluated in a subsequent Phase 3 clinical study.
3. If the difference in response rates between emricasan and placebo is more than 15%, then emricasan could be evaluated in a subsequent Phase 3 study.

These categories should not be interpreted as providing strict decision rules but rather as guidelines that will be factored into a broader scientific assessment of the benefit to risk profile for emricasan in this indication. This broader assessment will include consideration of secondary efficacy analyses, safety profile, and relevant information external to this study.

The operating characteristics for this three-category decision guideline are shown in Table 1.

Table 1. Operating Characteristics for Three-Category Decision Guideline

Probability of Obtaining an Estimated Treatment Effect (Emricasan – Placebo)			
True Treatment Effect (TE)	≤5%	5%≤ TE <15%	≥15%
0	67%	22%	11%
5	52%	26%	22%
10	36%	27%	37%
15	23%	24%	53%
20	13%	19%	68%
25	7%	13%	80%
30	3%	8%	89%

Note: Based on 100,000 simulations.

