4.2 Study Rationale

The Investigator's Brochure (IB) contains a summary of the data and information collected about IDN-6556 (including principal data and findings from preclinical, toxicological, and clinical studies conducted to date).

IDN-6556 is a novel small molecule irreversible caspase inhibitor. Caspases are enzymes responsible for executing apoptotic pathways, or programmed cell death, and activating cytokines such as IL-1 β and IL-18. The apoptotic pathway has been previously shown to play an important role in the formation and progression of hepatic fibrosis, leading to the hypothesis that inhibition of caspases may have significant therapeutic benefit for the treatment of liver fibrosis, independent of the underlying disease state (e.g., viral infection, fatty liver, etc.). Activation of pro-inflammatory cytokines such as IL-1 β has also been shown to play a role in hepatic injury. IDN-6556 has shown specificity in assays measuring caspase inhibition, and prevented apoptosis in a variety of cellular assays. IDN-6556 demonstrated efficacy in a number of animal models of liver disease, as well as in models of damage to other organ systems. Human studies have demonstrated that IDN-6556 can lower serum transaminases after intravenous or oral administration. Treatment with IDN-6556 was also associated with statistically significant reductions in elevated activated serum caspases and cCK18, a caspase cleaved substrate, indicating that IDN-6556 works by the presumed mechanism of action of inhibiting caspases.

In subjects who received a liver transplant and were successfully treated and achieved an SVR, fibrosis and inflammation were still present up to 5 years after treatment^{9,10,11}. In general, fibrosis stabilized or regressed in most subjects with increases in fibrosis in only a small subset of subjects. In general, inflammation/necro-inflammation was still present, but reduced as compared to pre-treatment. A caspase inhibitor, such as IDN-6556, could have clinical utility by reducing apoptosis rates and inflammation, which would also reduce the stimulus for fibrogenesis. Given this rationale, this study will evaluate the efficacy and safety of IDN-6556 in subjects with chronic hepatitis C virus (HCV) infection who have undergone

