12.5 Sample Size

The sample size determination for this study is based on the Phase 2b screening methodology presented in Fleming and Richardson¹².

A total of 60 subjects will be treated in a 2:1 ratio to IDN-6556 or placebo. Treatment duration for all subjects will be two years. The primary outcome variable is change in Ishak Fibrosis Score at 24 months.

The primary analysis of this Phase 2 “screening” study is formally based on a three-category decision guideline. To be specific, the decision guideline for this study is based on whether the proportion of subjects who show a regression (i.e., improvement) of Ishak Fibrosis Score at 24 months for the IDN-6556 arm compared to the placebo arm is less than 5%, is from 5% up to 15%, or is at least 15%.

Note that these categories should not be interpreted as providing strict decision rules but rather as guidelines that will be factored into a broader scientific assessment of the benefit to risk profile of the IDN-6556 regimen. This broader assessment will include consideration of safety, of secondary efficacy endpoints, and of relevant information external to this study. Specifically, the decision guidelines for this study are:

1. If the estimated absolute increase in the proportion of subjects who show regression in Ishak Fibrosis Score is less than 5%, (e.g., less than an estimated increase from 30% to 35%), then the IDN-6556 regimen is not plausibly more efficacious than placebo; the formulation of this IDN-6556 regimen or its utility in this indication will be reconsidered.
2. If the estimated absolute increase in the proportion of subjects who show regression in Ishak Fibrosis Score is from 5% up to 15%, (e.g., an estimated increase from 30% to between 35% and 45%), then the IDN-6556 regimen is

Title: A Multicenter, Double-Blind, Randomized Trial of IDN-6556 in Subjects Who had Hepatitis C Virus (HCV) Reinfection and Liver Fibrosis or Cirrhosis following Orthotopic Liver Transplantation for Chronic HCV Infection and Who Subsequently Achieved a Sustained Virologic Response Following anti-HCV Therapy

plausibly more efficacious than placebo and if analyses of biomarkers suggest utility of the IDN-6556 regimen, should be evaluated definitively in a subsequent Phase 3 clinical study.

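### SAP Section 4 widens response to include stable disease but keeps the 30% placebo rate and the operating-characteristics table built for regression, and that table follows no exact rule at differences of exactly 5% and 15%

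*SAP*

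**What the plan says.** Protocol 12.5 ties the guideline to "the proportion of subjects who show a regression (i.e., improvement) of Ishak Fibrosis Score at 24 months". Its worked examples start from 30%, for instance "less than an estimated increase from 30% to 35" per cent. Table 12.1 gives the chance of each category for true effects (TE) of 0 to 30 points.

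SAP Section 4 keeps the guideline but rests it on "the proportions of subjects who show a response (i.e., improvement or no change) per their Ishak Fibrosis Score at 24 months". SAP 5.1 is more precise: at baseline F2-F5, improvement or no change is a response; at F6, only improvement is. SAP 4 still states "The base case for the placebo response rate of 30% was assumed", citing a source that found 29%. Its Table 1 carries the same 21 percentages as Protocol Table 12.1, with the note "Note: Based on 100,000 simulations".

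SAP 9.1 judges study success by these criteria. Its cross-reference reads Section 0, but only Section 4 contains such criteria. SAP 14.1 presents the response-rate endpoint as bringing the analysis into line with the sample size calculation.

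The cut-offs are written four ways:

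| Place | Lowest | Middle | Top |
|---|---|---|---|
| Protocol 12.5 text | <5% | 5% up to 15% | at least 15% |
| Protocol Table 12.1 | <5% | >5% to ≤15% | >15% |
| SAP 4 text | <5% | 5% up to 15% | >15% |
| SAP Table 1 | ≤5% | ≥5% to <15% | ≥15% |

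For the top category the SAP text reads "If the difference in response rates between emricasan and placebo is more than 15" per cent, while the table head includes 15% itself.

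**The concern.** The definition of response was widened, but the placebo rate and the table that depend on it were not revisited. Protocol 4.2 says of transplant recipients who achieved SVR: "In general, fibrosis stabilized or regressed in most subjects with increases in fibrosis in only a small subset of subjects". A 30% rate of improvement-or-stable on placebo does not sit with that.

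A reader of SAP Table 1 will take 11% as the chance that an ineffective drug reaches the top category, and 23% as the chance that a true 15-point gain lands in the lowest. Neither figure was computed for the response that SAP 5.1 defines. In addition, a difference of exactly 5% or 15% has no single classification, so one result could be read as falling in either of two categories.

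**Working it through.** **Inputs.** 40 emricasan and 20 placebo subjects (SAP 3.3); placebo rate 30% (SAP 4); cut-offs 5% and 15%; F6 cap from SAP 3.2, "Up to 15 subjects with an Ishak score of F6 can be enrolled", which is 15/60 = 25%.

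**1. Reproducing the printed table.** Let x1 ~ Binomial(40, 0.30 + TE) and x0 ~ Binomial(20, 0.30). The difference is x1/40 − x0/20 = (x1 − 2·x0)/40, so it moves in steps of 2.5 points. Exactly 5% means x1 − 2·x0 = 2, and exactly 15% means 6. Full enumeration, comparing x1/40 − x0/20 with 0.05 and 0.15 in ordinary double precision, matches all 21 cells after rounding (largest gap 0.48 points). Examples: TE 0 gives 67.4/21.6/11.0 (printed 67/22/11); TE 15 gives 22.8/23.8/53.4 (printed 23/24/53). Among placebo rates of 20-70% in 1-point steps, only 30% matches all 21. The table is the 40:20, 30%-placebo table.

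**2. Boundary rule.** The same enumeration with ties assigned exactly, in integers, at 30% placebo:

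| Lowest / top rule | Cells matched | Largest gap (points) |
|---|---|---|
| <5 / ≥15 | 2 of 21 | 6.4 |
| <5 / >15 | 0 of 21 | 10.2 |
| ≤5 / >15 | 1 of 21 | 6.2 |
| ≤5 / ≥15 | 1 of 21 | 4.3 |

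At TE 0, 7.4% of trials fall on exactly 5% and 4.0% on exactly 15%. In double precision the 20 outcome pairs giving 5% split 10 low / 10 middle, and the 18 giving 15% split 7 middle / 11 top. Exact results at TE 0 are 61.2/25.1/13.6 (top ≥15%) or 61.2/29.2/9.6 (top >15%), against 67/22/11 printed. Under the SAP text rule the middle cell at TE 10 is 37.2%, against 27% printed.

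**3. What 30% implies for the new response.** By SAP 5.1, response rate = regression rate + share of all subjects who are stable F2-F5. If both rates are 30%, that share is 0%. With F6 at the cap and a fraction f of F6 improving, the F2-F5 response rate is (0.30 − 0.25f)/0.75:

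- f = 0: 0.30/0.75 = 40%, so 60% of F2-F5 placebo subjects worsen (9 of 15).
- f = 0.30: 0.225/0.75 = 30%, so 70% worsen.

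**4. Effect of a different placebo rate.** The documents give no rate for the new response, so a range is assumed. With F2-F5 responding at s = 80-90%, the overall rate 0.75s + 0.25f is 60-67.5% for f = 0 and 67.5-75% for f = 0.30; 80% is added as an upper case. Exact ties, <5 / 5 to <15 / ≥15:

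| Placebo | TE 0 | TE 15 | Largest shift from 30% |
|---|---|---|---|
| 30% | 61.2/25.1/13.6 | 19.1/26.4/54.4 | – |
| 60% | 61.2/23.5/15.3 | 19.3/27.1/53.6 | 1.7 |
| 70% | 62.2/24.1/13.8 | 16.9/29.5/53.6 | 3.5 |
| 75% | 63.0/24.6/12.4 | 14.8/31.6/53.6 | 5.6 |
| 80% | 64.2/25.2/10.7 | 11.7/34.8/53.6 | 8.4 |

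Shifts are in points over TE 0-20; at 80% the TE 20 row is left out because emricasan response would be 100%. If the top category is >15%, the shifts are 1.9/3.9/6.7/11.1. A TE of 30 is impossible above 70% placebo, and a TE of 25 above 75%.

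**The case against.** The strongest reply concerns consequence. Both documents call the categories guidelines rather than strict rules, and no alpha or stopping boundary rests on the table. The endpoint change is disclosed in SAP 14.1 and fully defined in SAP 5.1. At placebo rates up to about 70% the change of rate alone moves cells for TE 0-20 by under 4 points. The printed 11% lies inside the 10.7-15.3% found for placebo rates of 60-80% with the top category at ≥15%, and the printed 23% overstates the risk of dropping a useful drug. All of this stands and limits the practical effect.

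It is also fair that the source for 29% cannot be seen, so what it counted as a response is unknown; that Protocol 4.2 is qualitative; and that 60-80% is an assumption. The link between 30% and regression therefore rests on the protocol's own wording. But the protocol uses 30% for regression and the SAP uses 30% for a wider response, with an identical table. Both can hold only with no stable F2-F5 placebo subject.

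On ties, the diagnosis of double-precision comparison is an inference about code not shown, and the tie frequencies apply to complete data at exactly 40:20. With multiple imputation a pooled difference need not fall on the 2.5-point grid. That reduces how often a tie will arise in the real analysis. It does not explain a printed table that agrees with no exact rule, nor reconcile the SAP text with its own table head.

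**Conclusion.** The concern holds. SAP Table 1 describes regression at a 30% placebo rate, not the SAP 5.1 response, and it follows no exact rule at the two boundaries. SAP 14.1 is right that a binary endpoint matches the form of the sizing calculation, but the responder definition does not match.

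Two sizes should be kept apart. The boundary problem is present even for regression at 30%: at TE 0 the lowest category is 61.2% rather than 67% when exactly 5% counts as middle, and under the SAP text rule cells are off by up to 10.2 points. The effect of the wrong placebo rate is modest up to about 70% and grows above it, reaching 8.4-11.1 points at 80%; it rests on an assumed range. The case for correction is that the stated probabilities belong neither to the endpoint analysed nor to a defined rule. It does not depend on a claim that the study is mis-sized.

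The wording in SAP 4 that omits the F6 exception is a minor point, since SAP 5.1 governs through SAP 9.1 and 14.1.

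**What to change.** Before unblinding:

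1. In SAP 4, replace 30% with a justified placebo rate, or a range, for the Section 5.1 response.
2. Recompute Table 1 for it with one exact rule for differences of exactly 5% and 15%, worded identically in text and column heads. Use integer or rounded comparisons, and omit true effects that are impossible at the chosen rate.
3. Align the parenthesis in SAP 4 with the F6 rule of SAP 5.1, and point SAP 9.1 to Section 4.
4. Correct SAP 14.1 to say that the responder definition differs from the one used for sizing, and state whether the 5% and 15% cut-offs are kept for the new endpoint.

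The sponsor could instead apply the guideline to Month 24 regression as in Protocol 12.5 and report improvement-or-stable as secondary. That still needs one boundary rule and a recomputed table, and it costs more because it changes the endpoint that the guideline uses.

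The main fix costs SAP wording and one table. No new data are needed, because the three change groups are already derived. Sample size, the primary estimate and its confidence interval stay as they are; only the stated operating characteristics change.
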